5. STUDY INTERVENTIONS

5.1 Interventions, Administration, and Duration

5.1.1 Study Structure & Flow: Detailed study flow is illustrated in Figure 2 and Table 1 below, highlighting safety aspects where care in either arm differs from usual care, and the roles of ED providers and consultants in patient care in the intervention arm. The 30-day follow-up period after ED Index Visit will be the time window for analysis of primary endpoints. Although the VRT diagnosis and pathway decision will occur in real time, final adjudicated (correct) diagnoses will be determined by a masked, multidisciplinary panel of physicians using clinical data from the ED Index Visit, 1-week, and 30-day follow-up. Data from the 6-month follow-up (*funds permitting*) will not be used for primary trial outcome measures.

It is pre-specified that the VRT algorithm will be adjusted during the study period. Because this algorithm has not been used before in this specific study population, optimal cut points for various algorithmic parameters can only be approximated prior to the trial. The plan for adapting the algorithm will be refined during the logistical pilot study phase, in close concert with the study’s biostatistical team. The general plan is to adapt the algorithm frequently near the beginning of the trial, and progressively less frequently during the course of the trial. The algorithm will be adapted during the logistical pilot phase as frequently as necessary to identify cut points that maximize total diagnostic accuracy. The algorithm will be adapted during the main trial at pre-specified intervals that will be identified in the statistical analysis plan following the logistical pilot phase. In the event of

coding issues or algorithm malfunction, the system will default all patients to the Equivocal arm and the expert human VT double-check will ensure an appropriate VRT pathway is selected for the patient (see section 5.1.3).

5.1.2 Study Flow (timing): Patients will be directly engaged at three or four time points: (1) ED Index Visit, (2) 1-week clinic follow-up, (3) 1-month phone follow-up, and (4) 6-month phone follow-up. After consent, screening data collection burden early in the ED Index Visit is anticipated to be ~30-45 min. Additional research data will be gathered after patients are randomized (another ~30 min). In our prior observational studies,¹⁵ we have gathered research data from patients up to 60 min continuously. Total patient data collection burden in follow-up is anticipated to be approximately 6 hours, the bulk of which will occur during an on-site 1-week ‘gold standard’ follow-up visit: <1.5 hours for MRI; <3 hours for VOG, vestibular expert exam, repeating survey instruments; 1 hour for round trip travel; and 0.5 hours for 30-day telephone surveys. For scheduling purposes, the 1-week follow-up testing may be performed over two half days. Additional data will be gathered from the ED chart and electronic health record for the index visit and subsequent 30 days of follow-up. An additional phone follow-up will be made at 6 months to ascertain stroke diagnoses (*funds permitting*).

[figure not shown]

Figure 2. AVERT Trial flow (expanded). ED = emergency department; ENT = ear, nose, and throat physician; R = randomization; VOG = video-oculography; WK = week. VOG-guided rapid triage (VRT) selects one of three predetermined care pathways using decision rules implemented as a computer-based algorithm (detailed rules to be used and modified as needed):

a) If the VOG algorithm diagnosis is *peripheral*, the research team will request that the ED provider treat and discharge the patient, followed by same-day safety MRI. Treatment will be applied for VOG-based BPPV diagnoses by study personnel, while recommendations for medical therapies will be made for those with VOG-based other peripheral diagnoses (e.g., vestibular sedative treatments with or without steroid therapy for vestibular neuritis). ED providers may choose to go ‘off protocol’ and insist on admission for safety, and may choose to consult an ENT physician, vestibular physical therapist, or other provider (optional) for treatment of BPPV, vestibular neuritis, or other peripheral vestibular disorder. Safety MRIs will occur after an ED disposition decision is made (discharge, observation, admission). To optimize integration of VOG care pathways into local care delivery mechanisms, decisions regarding precise timing and location of immediate, same-day MRIs (<24 hours) were adapted to each site’s specific needs during the pre-trial logistical pilot phase.

b) If the VOG diagnosis is *equivocal*, the research team will request that the ED provider order a neurology consultation, with subsequent management determined by ED provider and consultant together. The requirement for neurology consultation may be waived in cases where doing so could not feasibly be accomplished within a reasonable time frame (e.g., at a site where on-site neurology consultation is not routinely available); in such a case, the ED provider would determine subsequent management without the assistance of a neurologist. ED providers may choose to go “off protocol” and consult an ENT physician, vestibular physical therapist, or other provider (optional) for treatment of BPPV, vestibular neuritis, or other peripheral vestibular disorder if they believe the patient has an inner ear disease.

c) If the VOG diagnosis is *central*, the research team will request that the ED provider order a neurology consultation, neuroimaging (MRI), and admit the patient for further evaluation and testing, even if the ED provider believes the patient has a peripheral cause; a note to this effect will be placed in the patient’s medical chart as part of the research record. The ED provider will make the final decision whether to admit the patient. If the ED provider elects to discharge the patient, this would be documented as a protocol deviation. The neurology consultation may be obtained after inpatient admission, if logistical circumstances in the ED or hospital so dictate. ED providers may choose to go “off protocol” and consult an ENT physician, vestibular physical therapist, or other provider (optional) for treatment of BPPV, vestibular neuritis, or other peripheral vestibular disorder if they believe the patient has an inner ear disease.

Table 1. Assigned care pathway group and associated VRT pathway and routine clinical care events

Assigned Clinical Pathway Group	Neurology consult at ED Index Visit	ENT or PT consult at index visit	Hospital admission at ED Index Visit	Same-day MRI (for safety)	Vestibular exam (1 wk)	Research MRI (1 wk)
VOG (peripheral)	Routine	Routine	Routine	Pathway (required)	Yes	Yes
VOG (equivocal)	Pathway (required*)	Routine	Routine	Pathway (required)	Yes	Yes
VOG (central)	Pathway (required*)	Routine	Pathway (required)	Pathway (required)	Yes	Yes
Standard care	Routine	Routine	Routine	Routine	Yes	Yes

ED = emergency department; ENT = ear, nose, and throat physician; PT = physical therapist; wk = week

* The requirement for neurology consultation in equivocal cases may be waived in cases where doing so could not feasibly be accomplished within a reasonable time frame; in such a case, the ED provider would determine subsequent management without the assistance of a neurologist..

Both Trial Arms (pre-randomization & follow-up): VOG exam determines eligibility

- patient approached for consent as early as possible during ED visit; randomization occurs after VOG testing
- algorithm exam protocol (HINTS-Hallpike-Hearing) is a ~20-minute data collection in the ED by the SC
- uses commercially-available recording equipment (portable VOG device, audiometer, tablet computer)
- examination protocol is standard in neuro-otologic specialty practice
- systematic 1-week (visit), 30-day (phone, records), follow-up post randomization

Trial Arm 1 VRT (intervention arm): VOG-based logic rules determine rapid triage pathway

- report includes direct device output (physiologic traces, quantitative measures) plus most likely diagnosis, category, and clinical trial care pathway (peripheral, equivocal, central) instructions
- the VOG results become part of the patient's clinical record

The roles of the ED provider in the care of patients in the VOG arm will be as follows:

- assess illness severity and appropriateness of the patient for VOG testing and the study protocol
- exclude obvious general medical conditions
- take over diagnostic decision-making for patients in whom VOG is equivocal (with consultant input, if available)
- intervene to deviate from VRT pathway if they are concerned about safety for patients in the VOG arm

Note: these are the same roles anticipated for ED providers if the VOG device were used for clinical practice

Trial Arm 2 Standard Care (control arm): usual ED care plus VOG exam, no VOG report generated

- no VOG automated interpretation or summary report will be generated; the computer-based randomization algorithm does not generate a VOG report or pathway using logic rules in the control (standard care) arm

The roles of the ED provider in the care of patients in the standard care arm will be as follows:

- assess illness severity and appropriateness of the patient for VOG testing and the study protocol
- exclude obvious general medical conditions
- all diagnosis, consultation, treatment, and disposition decisions will be made by the treating ED provider(s)

5.1.3 Expert Human VRT Double-Check: The VRT algorithm outputs in the intervention arm will be double-checked by expert neuro-otology fellows or faculty in real time to ensure accuracy; human judgment will “trump” VRT if there is disagreement (or if, for technical reasons, the real-time algorithm is not able to be generated – for example, as with internet connectivity problems or during development). The expert human double-check procedure will be in place at the start of the main trial, and we anticipate it will remain in place until the VRT algorithm is refined (as per pre-specified adaptations during the trial period) such that it appears accurate and safe.

Procedurally, the patient will be randomized electronically, with their VRT algorithm diagnosis determined electronically. If the patient is randomized to the VRT (intervention) arm, the on-call expert reviewer at the Coordinating Center will be notified (regardless of site) and the entire VOG recording will be available for immediate review and playback, in real time, along with key historical data. The review process is expected to take ~10-15 minutes. The review includes viewing a room camera of the test procedures, eye camera of the eye movements, and quantitative traces of eye and head. If necessary, the reviewer may contact the study coordinator to seek additional information. The double-check expert review procedure will NOT apply to those in the standard care arm (only those in the VRT arm).

In the VRT arm, the selected diagnosis is linked to the prespecified management recommendation per diagnosis. If the ED provider has any concerns with VRT-diagnostic category or specified management, they will be given the opportunity to talk with the reviewing vestibular specialist, if applicable, and if so desired. For as long as this human double-check procedure remains in place, any VRT-arm care recommended by the expert reviewer and endorsed by the ED physician will be considered clinically-indicated for billing purposes. For example, if the VRT algorithm suggests the patient has a vestibular neuritis, but the human reviewer changes the category to stroke, then the prespecified management pathways (including the stroke-related care) is considered clinically-indicated (e.g., ED index visit MRI, hospital admission). Alternatively, if the VRT algorithm returns an “equivocal” result and the expert reviewer changes the category to a specific vestibular condition, then the prespecified pathway for the vestibular condition (e.g., requires vestibular function testing for Menière’s disease) will also be considered clinically-indicated.

6. CLINICAL AND DEVICE-BASED TESTING

6.1 Schedule of Evaluations

Test/Procedure	Screening & Recruitment	ED Index Visit & Hospitalization	1-Week* Visit Follow-up (+/- 3 days)	Phone Follow-up 30 days (+/- 7) & 6 months (+/- 1)
Consent	X			
Symptom History				
Structured Symptom History	X		X§	X§
Vertigo Symptom Scale (VSS-SF)		X§		X§
ABCD ²	X			
Neurological Examinations				
NIH Stroke Scale (NIHSS)	X		X§	
Scale for the Assessment and Rating of Ataxia (SARA)	X		X§	
Calibrated Finger Rub Auditory Screening Test (CALFRAST)	X		X§	
Subjective visual vertical (SVV)		X§	X§	
Portable VOG (HINTS-Hallpike)	X		X	
Portable audiometry (air, bone hearing)		X§	X§	
Health Status Measures				
General Self-Rated Health	X		X	
Dizziness Handicap Inventory-Screening (DHI-S)		X	X	X
Modified Rankin Scale (mRSq)		X	X§	X
Neuro-QoL (multiple short form items)			X§	
RAND 36				X§
Charlson Comorbidity Index (CCI)		X§		X
MRI pre-screen	X		X (per local policies)	
MRI		X [†] (VRT arm)	X*	
Hospital admission		X‡ (VRT-C subarm)		
Neuro-otology examination			X	
Laboratory-based vestibular testing			X§	
Laboratory-based audiometry			X§	
EDPEC (satisfaction with overall experience)		X§	X§	
Resource utilization review		X	X§	X
Medical record review	X	X	X	X
Canalith repositioning treatment for active BPPV		X (VRT-P subarm)	X	
National Death Index review				X#

* Optimal timing for the follow-up Research MRI is days 3-7 after onset of symptoms, so timing of “1-week” follow-up will be scheduled accordingly.

§ Time permitting. Time constraints may make some of the testing, especially during the ED index visit, unrealistic under certain circumstances.

† MRI required for all participants in the VRT care arm (pathway MRI in VRT-C; safety MRI in VRT-P or VRT-E) unless ordered clinically; clinical MRI may or may not be ordered by the clinical care team for participants in the Standard ED-care (control) arm.

‡ Hospitalization may or may not be ordered by the clinical care team for any patient in either arm, but is pre-specified in the VRT-C subarm.

For patients lost to follow-up at 6 months, we will search the National Death Index to ascertain their vital status and cause of death, if available.

6.2 Timing of Evaluations

6.2.1 Screening & Recruitment: Screening & recruitment is the start of the screening process and begins when the study team identifies or is notified of a potentially eligible subject. Consent will be obtained prior to performing VOG to determine trial eligibility. The potential research subject will be informed as part of the consent discussion that the screening procedures will determine eligibility for the trial and that signing the consent form does not constitute enrollment into the trial.

6.2.2 ED Index Visit & Hospitalization: The acute phase of the protocol is defined as day one (day of randomization) through ED discharge or hospital admission. All subjects randomized to the VRT arm will undergo study-specific procedures as outlined in Table 1 above. Randomization, which is determined by the Vision EDC, will occur immediately after eligibility screening if all eligibility criteria are met.

6.2.3 1-Week Clinic Follow-up: The follow-up phase of the protocol begins during the week following the ED Index Visit. All enrollees will undergo a ‘gold standard’ battery of tests during week 1 that will be used in

determining final diagnoses. The tests will include a vestibular exam by a neuro-otologist, repeat VOG, caloric testing, formal audiology, and MRI as applicable. The timing of the Week-1 visit will be determined based on optimal MRI sensitivity for detecting stroke and logistical constraints. The optimal MRI timing window for diffusion-weighted images to detect stroke is roughly 3-7 days after the onset of continuous dizziness or vertigo symptoms, although MRI-DWI detects acute stroke with high sensitivity out to 14 days or longer. We will define “T0” (time zero) as the time when dizziness symptoms began or most recently worsened, leading to the ED index visit. We will define “T1” as the ED registration time at the ED index visit. Follow-up MRI should not occur prior to 72 hours after ‘T0’ to reduce the odds of a false negative follow-up MRI scan for those with stroke. The target window for MRI is 3-7 days after T0, but up to 14 days will be considered acceptable for the purposes of inclusion in the primary outcome analysis (see Statistical Analysis Plan below). If T0 is unknown or uncertain, we will use time from T1 to determine the appropriate follow-up window. For scheduling purposes, the 1-week follow-up testing may be performed over two half days, separated in time. Regardless of exact timing, this visit will be known as the “1-Week” or “Week-1” follow-up visit.

6.2.4 30-Day Phone Follow-up: All subjects will complete a phone interview 30 days (+/- 7 days) after the ED Index Visit. In the event that no 6-month follow-up is possible (e.g., due to funds limitations), the subject will be instructed that this is the final visit. 30-day phone follow-up (~20-30 min) will repeat symptom and quality-of-life measures (see Schedule of Evaluations) and determine hospitalizations or doctor visits for stroke-related diagnoses (e.g., stroke, aneurysm, heart attack). We will review relevant medical records for vascular events, outpatient visits (particularly neurology or otolaryngology), ED visits, hospitalizations, and neuroimaging. Regardless of exact timing, this visit will be known as the “30-Day” or “1-Month” follow-up visit.

6.2.5 6-Month Phone Follow-up: Funds permitting, all subjects will complete a phone interview 6 months (+/- 1 month) after the ED Index Visit. The subject will be instructed that this is the final visit. The 6-month phone follow-up and record review will be similar to the 30-day phone follow-up and record review in structure, but may be abbreviated. This visit is intended to provide data for a future Phase III trial with more longitudinal patient outcomes, and data at this time point will not be part of the AVERT Trial primary outcomes. For any patients lost to follow-up at this time point, we will search the National Death Index (<http://www.cdc.gov/nchs/ndi/index.htm>) using the patient’s social security number or other identifiers to determine the patient’s vital status and cause of death, if available.

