4.3.7 Masking (blinding): Allocation will be known to SC, ED provider(s), and patients (VOG result added to the medical record in the intervention arm), in order to guide management in the ED. This allocation will also be known to a small number of personnel at the CC, including members of the biostatistics team. The Investigator will become unmasked to allocation status for patients who have completed their final diagnosis adjudication as part of the iterative VRT algorithm refinement process (see Section 5.1.1). Since this is a diagnostic (not therapeutic) trial, masking is most crucial for outcome assessors, who will adjudicate final diagnoses ‘offline,’ masked to allocation status. Procedures will be used to ensure maximal masking of the Final Diagnosis Adjudication Committee (FDAC) members to trial allocation. In particular, all testing protocols are the same between the two arms of the study other than the required “safety MRI” in the VRT arm (Figure 1). The risk of unmasking of allocation therefore relates to patients in the standard care arm who do *not* undergo clinical MRI. The FDAC process will proceed in two discrete stages separated in time: (1) based solely on ED index visit data *without* the safety MRI; (2) based on all clinical data through the 30-day follow-up. Study radiologists will be masked to the index visit scan purpose/type (“safety MRI” vs. “pathway MRI” vs. “clinical MRI”), so the presence or absence of an imaging study will not cue them to the allocation during the first stage of FDAC review. During the second stage of review, study radiologists will reference any prior imaging studies using standard language that prevents disclosure to the other FDAC members whether a prior imaging study was or was not available (e.g., “The present study was compared to any prior studies, if available, and revealed no evidence of interval change.”). The actual FDAC review will occur approximately 1 month after these images are interpreted, so the neuro-radiologist, when reviewing this summary, will generally not recall which subjects did or did not have MRI imaging prior to the definitive, 1-week research MRI. If they do recall this information for a particular subject, they are instructed not to indicate this to the remaining FDAC members.

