6.3.19 Hospital admission: The ED provider determines if admission is necessary for the standard care pathway. The research team will request that the ED provider admit eligible subjects randomized to VRT whose VOG diagnosis is ‘central’ at the ED Index Visit. Those whose VOG diagnosis is ‘equivocal’ will have hospital admission determined by the ED provider in consultation with a neurologist, when available. Those whose VOG diagnosis is ‘peripheral’ will be discharged after safety MRI, unless the ED provider decides to admit ‘off protocol’ for safety.

6.3.20 Neuro-otology examination: All subjects will undergo a focused neuro-otology examination at the 1-week visit to evaluate ongoing and new clinical symptoms since the ED Index Visit, to assess the likely diagnosis, and to provide any necessary referrals or communication with other providers.

6.3.21 Laboratory-based vestibular testing: All subjects will undergo formal vestibular testing at the 1-week visit. This standard clinical vestibular testing battery (~3 hours) will include the following:

1. Subjective visual vertical (SVV) testing

This test requires the patient to re-position a mechanical light bar so it is oriented upright. Depending on site-specific procedures, this may occur using the ‘bucket test’ (described above).

2. Video-oculography (VOG) saccade accuracy testing

This test requires the patient to look from side to side.

3. Video-oculography (VOG) head impulse testing (vHIT), 6 semicircular canal planes.

This test involves ~15 rapid head rotations in the plane of each semicircular canal.

4. Video-nystagmography (VNG) with caloric testing.

This test involves a series of maneuvers designed to elicit nystagmus. These include looking side to side, blocking visual fixation, passive head shaking, positional tests (Dix-Hallpike, supine roll), and bithermal caloric testing (warm and cold water instilled into the ear canal) while supine.

5. Vestibular-evoked myogenic potentials (VEMPs), cervical (c-VEMPs) and ocular (o-VEMPs).

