Analytic approach: For all primary and linked secondary analyses, we will include only randomized subjects completing the essential elements of the diagnostic study protocol through the end of 1-week follow-up (i.e., with ED index visit VOG test results, follow-up MRI within 14 days, and an in-person neuro-otology visit within 30 days of the index visit). The quality of VOG and MRI testing will be determined by masked, expert raters from the FDAC during an FDAC meeting pre-review process; if either essential test is deemed to be of insufficient quality for analysis (e.g., key VOG tests performed improperly or missing; motion artifact on MRI), such patients will be excluded from the primary and linked secondary analyses of the main trial outcomes. This per-protocol analysis is appropriate for this Phase II study designed to determine the potential efficacy of the VRT intervention on diagnostic accuracy. Without adequate quality VOG and 1-week follow-up data, diagnoses will remain speculative. Subjects lost to follow-up at the 30-day time point (phone follow-up) will be included in these analyses, as 1-month medical record review will generally be sufficient to determine correct diagnoses.

Definitions: For the purposes of all analyses, the term “stroke” refers to any acute cerebrovascular event (ischemic stroke, transient ischemic attack, intracranial hemorrhage), unless expressly specified otherwise.

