2. STATISTICAL ANALYSIS PLAN

2.1 General Design Issues

Main trial design: Randomized controlled trial (individual patient randomization), parallel design (1:1). Results will be used for primary outcome analyses related to diagnosis accuracy at the ED index visit.

Secondary cohort design: Cohorts will be followed for adverse events and functional outcomes (1wk, 30d). Estimates will be used for phase 3 trial planning for the impact of diagnosis accuracy on clinical events and outcomes. The 6-month follow-up time point (if available) will not be part of the primary trial outcomes.

Observational arm: Patients with vestibular symptoms but no signs or who are not randomized for other reasons (see Inclusion and Exclusion Criteria) will be eligible for a parallel track observational sub-study with limited phone follow-up.

Diagnosis adjudication: Prior to adjudication, index VOG results will be interpreted by two independent vestibular experts masked to allocation. They will be given only patient demographic information, a structured summary of dizziness-related history of the present illness, and bedside hearing test results. Using this information, and masked to all other index visit clinical findings, ED physician diagnoses, any neuroimaging, and all follow-up data, they will render an ED index visit diagnosis (“Index VOG Diagnosis”). Prior to adjudication, MRIs will be interpreted by two independent neuro-radiologists masked to allocation and all clinical findings other than demographic information. They will render an index visit diagnosis (“Index Radiology Diagnosis”). A 5-member multidisciplinary panel with ED physician, otolaryngologist, vestibular neurologist, stroke neurologist, and neuro-radiologist will adjudicate diagnoses. The panel will be masked at all times to trial allocation (VRT vs. standard care). Diagnoses will be classified into 1 of 6 diagnostic categories likely to affect ideal ED management and rated as probable or definite based on neuroimaging results and standard clinical criteria. Diagnoses will be rendered in two stages – first based on VOG and all clinical data (including eye videos) from the ED index visit alone, without follow-up data (“Adjudicated Index Diagnosis”); then again after all 1-week testing and 30-day follow-up data are revealed electronically (“Adjudicated Final Diagnosis”). All differences will be resolved by discussion or majority vote.

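### The 1-week neuro-otology examination feeds the reference diagnosis, but nothing keeps the index diagnosis under test from the examiner, and no recusal step covers the real-time VRT reviewer

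*Protocol*

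**What the plan says.** Protocol 6.2.3 describes the 1-week battery that is used to settle final diagnoses: "The tests will include a vestibular exam by a neuro-otologist, repeat VOG, caloric testing, formal audiology, and MRI as applicable". Under 6.3.20 the examiner gives an opinion as well as findings, and also has a care role: "to assess the likely diagnosis, and to provide any necessary referrals or communication with other providers". Protocol 9.1 (Analytic approach) admits a patient to the primary analysis only with "an in-person neuro-otology visit within 30 days of the index visit".

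On who knows what, Protocol 4.3.7 says: "Allocation will be known to SC, ED provider(s), and patients (VOG result added to the medical record in the intervention arm". The arm descriptions in 5.1.2 add that in the VRT arm "the VOG results become part of the patient's clinical record", whereas in standard care "no VOG automated interpretation or summary report will be generated". The VRT report carries a most likely diagnosis and category.

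Masking is written for the adjudication panel and study radiologists (Protocol 4.3.7 and 9.1) and for the index VOG readers; SAP 2.1 repeats that "index VOG results will be interpreted by two independent vestibular experts masked to allocation". Neither document states the masking status of the 1-week neuro-otologist or limits what that examiner may read.

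The real-time check of the VRT output is done by neuro-otology fellows or faculty, and Protocol 5.1.3 limits it to one arm: "The double-check expert review procedure will NOT apply to those in the standard care arm (only those in the VRT arm". No recusal rule follows.

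**The concern.** The primary outcome scores the index diagnosis in each arm against the Adjudicated Final Diagnosis. If the person who supplies part of that reference already knows the diagnosis being scored, the reference can drift towards it. This is incorporation bias. Masking the panel to the arm does not remove it, because a panel that never learns the allocation can still receive an impression that the index diagnosis has shaped.

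The two arms need not be affected equally. A neuro-otologist may give more weight to a VOG diagnosis checked by a fellow specialist than to an ED provider's forced choice. The documents neither support nor exclude that. If it is so, the bias favours the trial's hypothesis when the arms are truly equal. The plan itself calls masking most important for outcome assessors, yet the only difference between arms that 4.3.7 treats as an unmasking risk is the safety MRI. The VRT report in the chart is not discussed.

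The related gap concerns the real-time reviewer, who knows the arm and may have set the VRT diagnosis that is scored (Protocol 9.1, Outcome assessment). That person could meet the same patient again at week 1.

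**Working it through.** **Tracing the route.**

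1. The examination is in the battery used for final diagnoses (6.2.3), and the panel sees all 1-week testing before the final stage (Protocol 9.1; SAP 2.1).
2. It carries weight. In the 6.1 schedule, laboratory vestibular testing and laboratory audiometry are marked time permitting; the neuro-otology examination is not.
3. Masked MRI reads protect stroke calls. They do much less for three peripheral categories, medical/other and non-diagnosis, which are five of the six categories scored.

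**Who is covered.**

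| Role | Masking to allocation stated? | Could the real-time VRT reviewer hold it for the same patient? |
|---|---|---|
| Panel member | Yes, at all times | Only in breach of the masking rule; no recusal step |
| Index VOG reader | Yes | Only in breach of the masking rule; no recusal step |
| Neuro-radiologist | Yes | Not relevant |
| 1-week examiner | Not stated | Nothing bars it |

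**The plan's own figure.** Inputs from Protocol 9.3: 90% versus 75%, alpha 0.05 (two-sided assumed), power 80%.

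- Uncorrected: n₀ = [1.96·√(2·0.825·0.175) + 0.8416·√(0.09 + 0.1875)]² / 0.15² = 99.5, so 100 per arm.
- Continuity-corrected: n = (n₀/4)·[1 + √(1 + 4/(0.15·n₀))]² = 112.5, so 113 per arm. This reproduces the plan. Masking or recusal would not change it.

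**Illustration 1: equal true accuracy p, pull in the VRT arm only.** Let b be the share of truly wrong VRT diagnoses to which the final diagnosis is pulled. No value of b is in the documents. Apparent VRT accuracy is p + (1 − p)·b. With 113 per arm and a two-sided 0.05 test without continuity correction, at p = 75%:

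| b | Patients moved (113·0.25·b) | Apparent VRT | Chance of rejection |
|---|---|---|---|
| 0 | 0 | 75% | 5.0% |
| 10% | 2.8 | 77.5% | 7.3% |
| 20% | 5.7 | 80% | 14.6% |
| 40% | 11.3 | 85% | 46.8% |
| 60% | 17.0 | 90% | 84.8% |

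The 20% row, for example: d = 0.05, s₀ = √(2·0.775·0.225/113) = 0.0556, s₁ = √((0.16 + 0.1875)/113) = 0.0555. The upper tail is Φ((0.05 − 1.96·0.0556)/0.0555) = 14.4%; the lower tail adds 0.2%. At p = 56%, b of 10% and 20% gives 10.3% and 27.1%; at p = 90%, 5.8% and 8.2%.

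**Illustration 2: pull in both arms.** Assume 10–30% of wrong VRT diagnoses and 5% of wrong ED diagnoses become correct.

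- Equal true accuracy of 80%: VRT 0.80 + 0.20·(0.10 to 0.30) = 82–86%; standard care 0.80 + 0.20·0.05 = 81%. Spurious gain: 1 to 5 points.
- Planning values: VRT 0.90 + 0.10·(0.10 to 0.30) = 91–93%; standard care 0.75 + 0.25·0.05 = 76.25%. The difference is 14.75 to 16.75 points against a true 15, a shift of −0.25 to +1.75 points. The sign turns where 0.10·g(VRT) = 0.25·0.05, that is at g(VRT) = 12.5%.

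**The case against.** The case on the other side is substantial and most of it stands as a limit on the point.

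- A reader might infer that the examiner is unmasked. The documents do not say so. The 4.3.7 list of people who know the allocation omits this clinician, and the Manual of Operations is not available here. What stands is silence on masking, alongside a chart and a patient that can both reveal the result.
- A reader might infer that the real-time reviewer is free to read the index VOG or sit on the panel. Protocol 9.1 and SAP 2.1 contradict that, since both roles must be masked. Also, 5.1.3 places the on-call reviewer at the Coordinating Center, which narrows where overlap with the 1-week examiner could arise.
- A reader might infer that only the VRT arm leaks. The ED diagnosis is the tested diagnosis in standard care and can be read there too.
- The examiner does not decide. Five masked members do, with two masked VOG reads, two masked MRI reads and eye videos, plus repeat VOG and laboratory tests where obtained. That the examiner's impression reaches them is the natural reading of the text but is not spelled out.
- One planned comparison cannot be touched by week-1 data: Preventable Six-Category Diagnosis Error uses the Adjudicated Index Diagnosis, which excludes follow-up (Protocol 9.2.1, secondary outcome 3; SAP exploratory outcome 1).

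None of this answers the remaining gap: following the plan as written lets the diagnosis under test inform its own reference.

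**Conclusion.** The point holds as a correctable gap in the protection of the primary endpoint. The documents neither mask the 1-week examiner nor restrict access to the index diagnosis, and that examination contributes to the Adjudicated Final Diagnosis. The result is a risk of differential incorporation bias, mainly outside the stroke calls. The recusal gap is complete for the 1-week examiner's role; for index VOG reading and the panel, the bar is implied but not enforced by any procedure.

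The size is unknown. Every rate used above is an assumption, and each treats a pull on the examiner as though it carried through the panel's vote, so the illustrations lean high for any given rate. On those terms the distortion is 1 to 5 points under equal true accuracy of 80%, and −0.25 to +1.75 points at the planning values. To create the whole 15-point design difference from a true 75% in both arms, 60% of wrong VRT diagnoses would have to be pulled. The documents therefore do not support a claim that the primary result will be biased by a known amount, or that the trial is invalid. The case for acting is that the remedy is cheap.

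**What to change.** **Protocol 6.3.20.** Require the examiner to record structured history, signs and diagnostic impression, and to lock that form in the EDC, before viewing the VRT report or the ED index diagnosis. Other index information needed for care and safety stays available throughout. Only the locked form goes to the panel.

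**Protocol 4.3.7.** State the 1-week examiner's masking status. Add a per-patient recusal flag so that whoever did the real-time VRT review cannot be that patient's 1-week examiner, index VOG reader or voting panel member.

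**SAP 2.2.** Name the Preventable Six-Category Diagnosis Error comparison as the sensitivity check on this point. It is clear of week-1 data, but its reference lacks the delayed MRI and rests on the index VOG. Agreement with the primary result would reassure; disagreement would not by itself show that the examiner was the cause.

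**Cost.** Wording, one EDC lock step and an assignment check. There is no new procedure and no change to 113 per arm. The index diagnosis is withheld for the first part of the visit, and case assignment needs a recusal check. A patient may still volunteer the result, so the leak is reduced, not closed.
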